include 100% juice). Frequencies and percentages will be used to describe categorical variables such as percent of students purchasing a sugary drink. Medians and interquartile ranges will be reported for continuous variables that exhibit skewness. Data will be descriptively summarized overall and by labeling strategy. All outcomes will be analyzed at the purchase level. The mean volume of sugary drinks at each two-week period will be modeled among the calorie label, text label, and graphic label arms by a linear regression model including intervention arm, two-week period, interactions of period and intervention arm and type of school (private or public) as independent variables. We will conduct exploratory analyses to examine whether usual frequency of sugary drink intake (high versus low) and biological sex moderate label effects. Examining only aggregate sales data could lead to incorrect inferences. Therefore, complementary individual-level survey data on purchases will also be collected. This aggregate/individual-level data combination will improve inferences about label effects. Although stratification by school type guarantees this variable will be balanced across our intervention arms, we are including it as a covariate in the model because it will enhance the precision of estimating intervention effects, as it explains variability in the outcome. The effectiveness of the interventions will be tested by evaluating the null hypothesis that the coefficients of the interactions of period and intervention are 0, indicating no change in the difference in volume of sugary beverages purchased across intervention arms from baseline. To account for clustering of purchases within schools, test statistics will be corrected using the variance inflation factor (VIF) as determined by the estimated intraclass correlation coefficient (ICC) for within school correlation. Primary and secondary outcomes in the calorie, text-based warning label, and graphic warning label arms will each be compared to one another. A Bonferroni-holm correction will be applied to control for multiple comparisons. We do not expect substantial missing data due to the point-of-sale technology we are using. The primary analysis will examine changes in labeled (sugary) and non-labeled beverages. Secondary analyses will examine changes for the following specific beverage categories: sugar-sweetened cola, sugar-sweetened sports drinks, sugar-sweetened lemonades/iced teas/juices, artificially-sweetened drinks (e.g., Diet Coke), milk, 100% fruit juice, unsweetened coffee/tea, and bottled water. For the survey data, we will conduct similar linear regression analyses to compare total mean kcals purchased among intervention arms.

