### **Primary outcomes:**

1. Fluid ounces of SSBs purchased per sales transaction
  - a. SSBs= any beverage with more than 5g/100mL of sugar reported in the NFP
2. Total beverage calories purchased per sales transaction
  - a. Beverage calories= any calories coming from beverages (SSBs and non-SSBs)

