### **Description of data:**

The first is a longitudinal data set (at the school level) of store purchases from July – August 2019 obtained by trained research assistants in three schools located in Guatemala City. Data are daily purchases of food items and beverages by students. Sample is total purchases obtained from scanning products' barcodes or using an application (Square app) to assign unique codes to products without a barcode. Data include food purchases, brand, flavor, size, and quantity. Additionally, an inventory of beverages' brand, flavor, price, size (mL), serving size (mL) as reported in the Nutrition Facts Panel, calories (kcal), total fat (g), saturated fat (g), total carbohydrates (g), sugar (g), sodium (mg), protein (g), ingredients, total sugar, sodium, and protein per container (g).

The second dataset is an intercept survey conducted with students after they made a purchase at the school store. Data include total expenditure, number and type of items purchased (i.e., beverage, food, or non beverage/food item), perception of healthfulness of

specific beverages (i.e., water, fruit drink, soft drink, light soft drink), and the label awareness, recall, use, and trust. Usual SSB consumption, demographics, height, and weight are also included in the survey.

For our primary analysis, we will look only at the 2 schools which were randomly assigned to condition (one treatment and one control school).

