### **Statistical analysis:**

- Consistency of data: We will conduct analyses to check the consistency of categorical data, including frequency tables and chi-square tests (i.e., purchase type, beverage type, healthfulness perception, label awareness, and demographic variables). To check the consistency of continuous variables, we will create box plots of mean size by beverage categories (SSBs, non-SSBs), purchased quantity, price, volume purchased, serving size, calories, and expenditure.
- Outliers: Within each beverage category (SSBs, non-SSBs), we will examine purchases in the 99th percentile and above (by volume and total calories) to identify any beverage purchases that seem implausible. For the survey data, we will exclude any expenditures that appear implausible.
  - o Data will be pooled (across conditions) when assessing for quality so that we are blind to which condition outliers are in. We will ask the school stores and research assistants to clarify any values that appear out of range prior to excluding any data. Any data that are excluded will be done prior to re-matching data points to their condition.
  - o We will exclude any individual-level data from our customer purchase assessments if no school cafeteria purchase was recorded.
  - o We will exclude any customer purchase assessments if they include implausible purchases (e.g., items not sold at the store). Although we expect to have minimal missing data, we will consider other analytic techniques to handle missing data if the amount is greater than 10%.
- Descriptive analysis: We will summarize (i.e., mean, SE, trends) the primary and secondary outcome variables by condition and time period (pre- or post-). We will also examine changes in primary and secondary variables.
- Statistical design: We will use a difference-in-differences approach to examine the effect of the posters taking into account pre-treatment differences between the treatment and control groups and time trends (pre- and post-). The basic equation for this approach is:

$$Y_{it} = \eta + \gamma d_i + \delta T_t + \alpha d_i * T_t + u_{it}$$

Where  $d_i$  is a binary variable equal to 1 if they were exposed to the poster, 0 otherwise,  $T_t$  is a binary variable equal to 1 in the post period and 0 in the pre period,  $d_i * T_t$  is an interaction term between the two, and  $\alpha$  is the difference-in-differences estimator.

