- The effectiveness of the intervention will be tested by evaluating the null hypothesis that the coefficient of the interaction of time period and intervention is 0, indicating no change in the fluid ounces of SSBs purchased and beverage calories purchased between conditions.
- Regarding the secondary outcomes, we will present the percentage of all transactions and all beverage transactions that include an SSB by condition and time period. To

calculate the total calories per transaction, we will use the Nutrition Facts Panel data of each food or beverage product.

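### The SAP tests effectiveness on single transactions with no school-day term and no standard-error method, so any store-specific day-to-day variation would make the standard error too small

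*SAP*

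**What the plan says.** The SAP (Primary outcomes) lists "Fluid ounces of SSBs purchased per sales transaction" and "Total beverage calories purchased per sales transaction". The protocol's Analysis Plan has the same unit: "All outcomes will be analyzed at the purchase level".

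The SAP (Description of data) says of the sales file: "Data are daily purchases of food items and beverages by students". The primary analysis is limited to the two randomised schools, one per condition.

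The difference-in-differences equation (SAP, Statistical analysis) contains a condition indicator, which "is a binary variable equal to 1 if they were exposed to the poster, 0 otherwise", a period indicator, their product and one error term. Effectiveness is judged by "evaluating the null hypothesis that the coefficient of the interaction of time period and intervention is 0". The SAP has no term for the day or school-day, no aggregation to days, and no clustered, robust or other variance method. It states neither alpha nor sidedness.

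The protocol's Analysis Plan did include a clustering correction: "To account for clustering of purchases within schools, test statistics will be corrected using the variance inflation factor (VIF". It was to be based on the estimated within-school ICC. The SAP does not restate it.

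**The concern.** Transactions in one store on one day share that day's stock, menu and timetable. They are therefore likely to resemble each other more than transactions from different days. An analysis that treats each transaction as independent counts a day's common swing once for every purchase made that day.

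The interaction test is the SAP's only test of effectiveness for either primary outcome. If its standard error is too small, ordinary day-to-day variation in one store can appear as a significant poster effect on ounces of sugary drinks or on beverage calories, and any interval would be too narrow.

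This differs from the lack of replicate schools. That limit concerns a lasting change in one school, and these data cannot cure it. The present point concerns transient day-level variation, which daily sales records allow one to estimate.

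**Working it through.** **The plan's own figures.** The SAP gives no sample size, power or alpha for this test, so there is nothing to reproduce. The protocol's 82% power for differences of 0.21 SD with 500 per arm does reproduce (82.3% for one pairwise comparison at two-sided 0.05/3). It belongs to the three-arm survey design and does not bear on this point.

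**Inputs from the documents.** Two schools, one per condition; two periods (pre and post); outcome per transaction; no variance method.

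**Assumed inputs.** Two-sided 5%; m = 50, 100 or 200 transactions per school-day; day-level ICC ρ = 0.005, 0.01 or 0.05; days independent of each other; share s of the day shock common to both schools = 0 or 0.5.

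**Formula.** Take the transaction variance as 1, with D sales days in each of the four school-by-period cells.

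- Variance assumed by the transaction-level test: 4/(mD).
- Actual variance of the estimate: (4/D) × [(1 − s)ρ + (1 − ρ)/m]. The shared part cancels between schools if both sell on the same days.
- Ratio: V = 1 − ρ + m(1 − s)ρ. This is 1 + (m − 1)ρ when s = 0 and 1 + (m/2 − 1)ρ when s = 0.5. D drops out.
- Type I error: 2 × [1 − Φ(1.96/√V)].

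Example: m = 100, ρ = 0.05, s = 0 gives V = 1 + 99 × 0.05 = 5.95, √V = 2.44, and a type I error of 42%.

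| ICC | Shared | m = 50 | m = 100 | m = 200 |
|---|---|---|---|---|
| 0.005 | none | 8% | 11% | 17% |
| 0.005 | half | 6% | 8% | 11% |
| 0.01 | none | 11% | 17% | 26% |
| 0.01 | half | 8% | 11% | 17% |
| 0.05 | none | 29% | 42% | 55% |
| 0.05 | half | 19% | 29% | 42% |

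With ρ = 0, V = 1 and the error is 5%. Over wider assumptions with no sharing (m = 25 to 500, ICC 0 to 0.10), the formula runs from 5% to 78%.

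**Simulation.** With 10 or 20 days per period and 4,000 runs per setting, the transaction-level test matched the formula: 17-18% at m = 100, ICC 0.01, and 54-55% at m = 200, ICC 0.05, both without sharing. In the same runs a test on school-day means rejected 4.4-6.1% of the time. A test on the daily difference between schools gave 4-6% with independent days. With day-to-day autocorrelation of 0.3 it reached up to 14% before any serial-correlation correction.

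**Would the protocol's correction have helped?** It addresses correlation within schools, not within days. With one school per condition, the school indicator equals the condition indicator, so a between-school ICC cannot be separated from the condition effect.

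**The case against.** The case against has five parts.

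- **The independent-errors test is inferred.** The SAP presents its equation as the basic one, describes the data as longitudinal at school level, and indexes the outcome by unit and time. An unstated day-level or clustered analysis is possible. This stands in part: the SAP leaves the variance method unspecified and does not choose a wrong one. But with outcomes defined per transaction and nothing further stated, ordinary regression on transactions is the default reading.
- **The large figures need a strong assumption.** ICC 0.05 means a day-level SD of √0.05 = 0.22 transaction SDs, about the size of the 0.21 SD that the protocol calls a small difference between conditions. Weather and similar shocks would be largely common to two schools in one city and would cancel. This stands. A reader might infer that the false-positive rate simply is 19-55%, but that range arises only at the highest ICC in the table, and the documents neither support nor exclude that value.
- **Nothing protective was lost.** A reader might infer that the SAP removed a correction that would have handled the problem. The documents do not support that: the protocol's factor concerned schools.
- **Pairing by day is not documented.** The SAP gives a July-August 2019 window. It does not say that both stores sold on the same days or changed period together. This stands and limits the paired version of the fix.
- **The gain is limited.** With a school-specific shift between periods of SD 0.02, 0.05 or 0.10 (in transaction SDs; m = 100, ICC 0.02, 10 days per period), a day-level test still rejected 6%, 14% or 34% of the time in simulation. This stands and must be disclosed, but it is no reason to leave a second, avoidable source of error.

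**Conclusion.** The concern holds in conditional form. The SAP's test is on transactions, with no school-day term and no standard-error method. Followed as ordinary regression, it gives standard errors that are too small whenever there is store-specific day-to-day correlation. The direction is certain; the size is not.

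Under the assumptions in the table, the type I error is about 6-17% at ICC 0.005, 8-26% at 0.01 and 19-55% at 0.05. The lower ends apply with 50 transactions per school-day and half of the day shock shared. The upper ends apply with 200 transactions and nothing shared. Without store-specific day variation there is no inflation.

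A reader might also infer that calendar-day effects common to both stores would solve this. They would not: such effects absorb what the stores share, which already cancels when sales days match, and leave the store-specific swings that cause the inflation.

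The SAP should be changed before the test is relied on. Confidence in the size is only moderate, because every quantitative input is assumed.

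**What to change.** In the SAP's Statistical analysis section, keep both outcomes per transaction and make the school-day the unit of inference.

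- **If both stores sold on the same calendar days:** compute each school's daily mean per transaction and take poster school minus control school. Test the pre-to-post change in that difference, with degrees of freedom set by the number of days and a standard error that allows for serial correlation (for example AR(1) or Newey-West). The correction should be checked for the number of days available, since its performance was not simulated here.
- **Otherwise:** use school-day means, errors clustered by school-day, or a school-day random effect.
- **Weighting:** state whether days are weighted by their number of transactions. Equal weighting gives quiet and busy days the same influence and moves the target away from the mean per transaction.
- **Calendar-day effects:** if included, do not rely on them alone.
- **Scope of the interval:** state that it covers day-to-day variation only and cannot separate a lasting school-specific change between periods from the poster effect.
- **Test level:** state alpha and sidedness.

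The cost is SAP wording and a short aggregation of sales already recorded daily; no new data are needed. Intervals will be wider, days on which only one store sold are lost if pairing is used, and the weighting choice must be declared in advance.
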